6.10.2 Primary Outcome and Methodology

Analysis of the primary endpoint (SRI-4 at the Week 52 visit) is described in [Table JAIA.6.4](#) and [Table JAIA.6.6](#). The primary analysis will utilize logistic regression (as described in Section 6.4) with NRI and multiple imputation (as described in Section 6.4.2.1 and Section 6.4.2.4). The estimand of interest to assess the population-average effect (odds ratio) attributable to the medication to which patients are initially randomized, if no ‘rescue’ medications were available, in a pandemic-free environment. This estimand is free of confounding effects of increase in concomitant medication use (namely, increases in use of corticosteroids above the baseline dose other than the permitted corticosteroid burst/post-taper increase, and/or initiation of or an increase above baseline dose in immunosuppressant or antimalarial treatment).

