5.2 Determination of Sample Size

Study JAIA will randomize approximately 750 patients with a 1:1:1 ratio between baricitinib 4-mg, 2-mg, and placebo. The proposed sample size will ensure >90% power to detect an absolute difference of 17% between a baricitinib treatment group and the placebo treatment group assuming a 40% placebo response rate for the primary endpoint using a 2-sided α of 0.05. The anticipated effect size represents a clinically relevant difference.

Sample size and power estimates were obtained from nQuery® Advisor 7.0 using the χ^2 test of equal proportions.

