6.4.2.1 Non-responder Imputation (NRI)

The non-responder imputation (NRI) method may be used when the estimand of interest uses the composite strategy (EMA 2020) for handling intercurrent events. In this strategy, patients will be considered non-responders for the NRI analysis if they do not meet the clinical response criteria or have missing clinical response data (based on each set of [Table JAIA.6.5](#)) at the analysis time point.

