PPCV	
For patients experiencing the ICEs of treatment discontinuation, study discontinuation, or prohibited medication use, observations after such ICEs will not be included in analysis (that is, will be considered as missing).
 
Data from patients experiencing treatment interruptions due to non-COVID related interruptions, such as, adverse events or abnormal labs, etc., will be included and used as is, per treatment regimen.
 
Data from patients experiencing off-drug interruptions 20 or more days due to COVID-19 will not be included (that is, will be considered as missing) until treatment resumption of 20 days or more.
	Addresses the clinically relevant question comparing the number of subjects able to both complete the study treatment and to achieve adequate response without further medication being required in a pandemic-free world. Targets treatment effect without potentially confounding influences of COVID-19.
PP	
For patients experiencing the ICEs of treatment discontinuation, study discontinuation, or prohibited medication use, observations after such ICEs will not be included in analyses (that is, will be considered as missing).
 
Data from patients experiencing treatment interruptions due to non-COVID related interruptions, such as, adverse events or abnormal labs, etc., will be included and used as is, per treatment regimen.
 
Data from patients experiencing off-drug interruptions due to COVID-19 will be included and used as collected.
	Addresses the clinically relevant question comparing the number of subjects able to both complete the study treatment and to achieve adequate response without further medication being required.
AC	
For patients experiencing the ICEs of treatment discontinuation, prohibited medication use, or COVID-19 off-drug assessments, observations after such ICEs will be included in analyses until the study discontinuation or the date of the Week 52 visit, whichever earlier.
 
The post-treatment follow-up period will not be included in the efficacy analysis.
	Addresses the clinically relevant question comparing the number of subjects able to achieve adequate response, regardless of adherence and treatment compliance, in resemblance to real-world expectations.

Abbreviation: AC = as collected; ICE = intercurrent events; PP = per protocol; PPCV = per protocol COVID free.

Table JAIA.6.6. Description of Efficacy/Health Outcomes Analyses

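### Section 6.10.2 describes the primary estimand as a population-average, no-rescue odds ratio, but the planned analysis is composite for rescue and gives a conditional odds ratio

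*SAP*

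**What the plan says.** Section 6.10.2 gives the primary estimand in words: "The estimand of interest to assess the population-average effect (odds ratio) attributable to the medication to which patients are initially randomized", under the condition that no rescue "medications were available, in a pandemic-free environment". It adds that this estimand is free of confounding by increases in corticosteroids, immunosuppressants or antimalarials. It does not mention treatment discontinuation. The same paragraph assigns the analysis: logistic regression with non-responder imputation (NRI) and multiple imputation (MI).

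Other sections describe what that analysis does:

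- **Section 6.4.2.1:** NRI "may be used when the estimand of interest uses the composite strategy". Section 6.4.2.2 keeps the hypothetical strategy for MMRM.
- **Section 6.4.2.4:** data after prohibited medication, or after discontinuation for non-COVID reasons, count as missing for non-COVID reasons. They are handled by NRI for binary endpoints. MI covers only what is missing because of COVID-19.
- **Table JAIA.6.5, PPCV datapoint set (used for the primary analysis):** the question compares the numbers of patients "able to both complete the study treatment and to achieve adequate response without further medication being required in a pandemic-free world".
- **Section 6.4:** primary inference uses the odds ratio from a Firth logistic model with treatment, baseline SLEDAI-2K stratum, corticosteroid stratum and region. No standardisation step is given.

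**The concern.** Two properties claimed in Section 6.10.2 are not properties of the planned analysis.

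**Handling of rescue.** An effect in a setting without rescue is a hypothetical strategy. It asks what patients who took rescue would have achieved without it. NRI does not ask that. It makes the use of rescue part of the outcome, as a failure. The two agree only if no such patient would have responded without rescue, which the SAP neither states nor justifies.

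**Type of odds ratio.** Odds ratios are non-collapsible. When covariates predict response, the treatment odds ratio from a model containing them differs from the population-average one even under perfect randomisation.

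At stake is interpretation. Section 6.10.2 is the section on the primary outcome and is a natural source for the report's description of the effect. A result described in its words would be read as a no-rescue effect averaged over the population. The analysis gives the odds ratio, within covariate strata, for completing treatment without clinically significant prohibited medication and responding.

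**Working it through.** **1. The plan's own figure.** Section 5.2: "Study JAIA will randomize approximately 750 patients with a 1:1:1 ratio between baricitinib 4-mg, 2-mg, and placebo", so 250 per arm. The claim is ">90% power to detect an absolute difference of 17% between a baricitinib treatment group and the placebo treatment group". Its other inputs are 40% response on placebo and two-sided testing at the 5% level; the method is the χ² "test of equal proportions". With p0 = 0.40, p1 = 0.57 and mean p = 0.485:

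z = [0.17·√250 − 1.96·√(2·0.485·0.515)] / √(0.40·0.60 + 0.57·0.43) = (2.688 − 1.385)/0.696 = 1.87, so power is 96.9%.

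Ninety per cent power needs 180 per arm (192 with continuity correction). The stated power is met. Read as composite response rates, 40% and 57% still give 96.9%, so correcting the wording changes no sample size.

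**2. Marginal odds ratio at the design rates.** (0.57/0.43)/(0.40/0.60) = 1.99.

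**3. Conditional against marginal.** The SAP gives no covariate effects, so these are assumed: two binary strata split 50:50 and five equal regions, giving 20 equally weighted cells with log-odds offsets c. Solve for a so that the mean of expit(a + c) is 0.40, then for d so that the mean of expit(a + d + c) is 0.57. The conditional odds ratio is exp(d).

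| Assumed stratum OR (each) | Assumed region log-odds range | Conditional OR | Marginal OR | Ratio of log ORs |
|---|---|---|---|---|
| 1.5 | ±0.3 | 2.03 | 1.99 | 1.03 |
| 2 | ±0.5 | 2.11 | 1.99 | 1.09 |
| 3 | ±0.8 | 2.29 | 1.99 | 1.20 |

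**4. Composite against no-rescue.** Hold the composite rates at 40% and 57%. For each arm, no-rescue rate = composite rate + (share with an event) × (share of those who would have responded without rescue). Neither share is in the SAP, so all are assumed.

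| Event share, placebo / active | Would respond, placebo / active | No-rescue rates | Difference (points) | OR |
|---|---|---|---|---|
| any | 0 / 0 | 40% / 57% | 17 | 1.99 |
| 20% / 20% | 20% / 20% | 44% / 61% | 17 | 1.99 |
| 25% / 15% | 20% / 20% | 45% / 60% | 15 | 1.83 |
| 30% / 30% | 20% / 30% | 46% / 66% | 20 | 2.28 |
| 30% / 30% | 30% / 40% | 49% / 69% | 20 | 2.32 |

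For the third row: 0.40 + 0.25·0.20 = 0.45, 0.57 + 0.15·0.20 = 0.60, and (0.60/0.40)/(0.45/0.55) = 1.83. Across all scenarios tried, the no-rescue odds ratio ran from 1.83 to 2.32.

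**5. The test.** With no treatment effect within any stratum, the conditional and marginal odds ratios both equal 1. The label therefore does not affect the primary test or its type I error.

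**The case against.** The best defence is that Section 6.10.2 is not where the SAP places its estimand. Section 4 sends the reader to Section 6.4.2 and Table JAIA.6.5 for intercurrent events and to Table JAIA.6.6 for the summary measure. Sections 6.4.2.1 and 6.4.2.4 and Table JAIA.6.5 fit together as a hybrid: composite for rescue and discontinuation, hypothetical for COVID-19. That is right, and it means the analysis itself is coherent. It also means that Section 6.10.2 contradicts the governing text. For the summary measure, Table JAIA.6.6 names only logistic regression, so Section 6.10.2 is the only place that says which kind of odds ratio is meant.

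A second defence is that the conditional/marginal gap is minor. Section 6.10.3.3.1 expects adjusted and unadjusted odds ratios to be similar, from Phase 2 data. Section 6.4 also reports an unadjusted difference in percentages, descriptively. Both bear on size and support a modest reading, but neither makes the label correct. The rescue mismatch does not depend on them.

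A reader might infer more than the SAP supports:

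- **That every user of prohibited medication is a failure.** Section 6.9 and the footnote to Table JAIA.6.2 exempt changes judged not clinically significant on blinded review.
- **That Table JAIA.6.5 itself uses the term composite.** It describes such a question but does not use the word. Section 6.4.2.1 does.
- **That the mismatch flatters the drug.** The direction depends on rates the SAP does not give.

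**Conclusion.** The point holds as a misstatement of the primary estimand. Section 6.10.2 claims a no-rescue, population-average odds ratio. The analysis delivers a composite for clinically significant prohibited medication and for non-COVID discontinuation, a hypothetical treatment of COVID-19 events only, and an odds ratio conditional on the model terms.

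It would be too strong to conclude that the primary analysis is invalid. The p-value, type I error and sample size stand, and the pandemic-free part of the wording matches the MI.

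Against a marginal odds ratio of 1.99 at the design rates, the conditional one is about 2.03 to 2.29 (3% to 20% larger on the log scale) and the no-rescue one about 1.83 to 2.32. Both ranges rest on assumed inputs. The rescue gap can take either sign and is nil if patients with such events would not have responded without rescue. What changes is the claim that can be attached to the estimate.

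**What to change.** Reword Section 6.10.2 to agree with Sections 6.4.2.1 and 6.4.2.4 and Table JAIA.6.5:

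- **Composite strategy:** prohibited medication as classified by the blinded review, and treatment or study discontinuation not due to COVID-19 logistics.
- **Hypothetical strategy:** only COVID-19 events not related to infection. Section 6.1 limits the COVID-19 accommodations to these, and Section 6.7 classes discontinuation for COVID-19 infection as due to an adverse event, so it stays composite. Stating this boundary keeps any discontinuation from falling under both strategies.
- **Summary measure:** label the Firth model odds ratio conditional and keep it for the p-value.

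Because the SAP names a population-average effect as its target, also report a standardised marginal odds ratio and risk difference. Take them from the same fits by averaging each patient's predicted probabilities under each treatment, with delta-method or bootstrap variance, and pool by Rubin's rules over the 25 imputed data sets. If that is not wanted, delete the term population-average.

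The cost is a few lines of SAP text and, if the marginal estimate is kept, one post-estimation step per imputed data set. The primary test and the sample size do not change.

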6.10.3 Secondary Efficacy Outcomes & Methodology

6.10.3.1 Secondary Efficacy Analyses

The analysis of the major secondary endpoints is described in [Table JAIA.6.4](#) and [Table JAIA.6.6](#) and Section 6.4. The list of major secondary endpoints may be found [Table JAIA.4.1](#). A multiple testing procedure will be utilized to control the FWER at the 0.05 significance level for principal inference of the primary endpoint and all major secondary endpoints (see Section 6.7).

6.10.3.2 Other Secondary Efficacy Analyses

The analysis of the other secondary endpoints is described in [Table JAIA.6.6](#).

6.10.3.3 Supplementary and Sensitivity Analyses

Supplemental analyses based on all observed data will be provided for all primary and major (multiplicity controlled) endpoints:

- AC analyses will include all data collected from randomization through the Week 52 visit, regardless of treatment discontinuation, prohibited medication use or treatment interruption; this analysis does not address a pandemic-free estimand.
- PP analyses are planned to target the estimand not free from the confounding effects of the pandemic.

6.10.3.3.1 Tipping Point Analyses

Planned tipping point analyses will be conducted provided the associated nominal p-value is significant. An interpretation of clinical plausibility of the assumption underlying the tipping point will be provided. This analysis will be performed on SRI-4 at the Week 52 visit to assess the robustness of the primary analysis.

Based on the evaluation of baricitinib SLE Phase 2 data (Study JAHH), the adjusted odds ratios are expected to be similar to unadjusted odds ratios, and therefore the tipping point analyses will be unadjusted for covariates. In this analysis, patients who have not had a treatment failure, but are missing data at the Visit 16 (Week 52) time point, will have their response status changed from not achieving response to achieving response, in an iterative manner.

At each step of the analysis, one subject will be switched from not achieving SRI-4 response to achieving SRI-4 response and the analysis re-run. The results (statistical significance) will be presented in a grid where the x-axis and y-axis represent the number of subjects assumed to achieve SRI-4 in the placebo group and the given baricitinib treatment group, respectively. The region where the conclusion changes will be considered as the tipping point.

The grid will be divided in 3 regions, limited in the top by the expected number of subjects from the baricitinib treated arm that could have achieved SRI-4 had they had sufficient data and could have achieved SRI-4 response, and limited from the right by the number of subjects in the equivalent placebo group.

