6.4 Analysis Methods

The family-wise type I error rate (FWER) will be controlled at a 0.05 significance level for primary and major secondary endpoints using a prespecified graphical procedure (see Section 6.6). Unless otherwise specified, all other hypothesis testing will be conducted at a nominal significance level of 0.05.

For assessments of the primary endpoint and other binary efficacy and health outcomes endpoints, the following will be provided unless otherwise specified:

- Observed percentage for each treatment group along with the corresponding 2-sided 95% confidence interval (CI)
- The difference in percentages and 95% CI using the Newcombe-Wilson method without continuity correction, used for descriptive purposes
- The p-value and 95% (unless otherwise specified) CI for the odds ratio from the logistic regression model, used for primary statistical inference. The model will include the following explanatory variables: treatment, baseline disease activity (total SLEDAI-2K <10; ≥ 10), baseline corticosteroid dose (<10 mg/day; ≥ 10 mg/day prednisone or equivalent) and region (North America, Central/South America/Mexico, Europe, Asia and Rest of World). A Firth penalized likelihood will be used (Firth 1993), and
- If deemed necessary, additional analyses of categorical efficacy variables will be conducted to address sparse data or small sample sizes. The Fisher's exact test will be utilized if necessary.

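### The SRI-4 tipping-point grid is opened and, by default, judged at nominal 0.05 rather than at the level of the graphical procedure, and its placebo limit is ambiguous

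*SAP*

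**What the plan says.** SAP section 6.10.3.3.1 sets the condition for running the analysis: "Planned tipping point analyses will be conducted provided the associated nominal p-value is significant". Patients without treatment failure who lack Week 52 data are then switched one at a time from non-responder to responder. Statistical significance is displayed with placebo counts on the horizontal axis and baricitinib counts on the vertical axis, without covariate adjustment. The tipping point is the region where the conclusion changes. No significance level is attached to the cells. Section 6.4 supplies the only default: "Unless otherwise specified, all other hypothesis testing will be conducted at a nominal significance level of 0.05".

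The grid is to be split into three regions, which are not defined further. It is "limited in the top by the expected number of subjects from the baricitinib treated arm that could have achieved SRI-4" and "limited from the right by the number of subjects in the equivalent placebo group". No response rate or method is given for the expected number.

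Table JAIA.4.1 lists SRI-4 at Week 52 as the primary endpoint for 4 mg and as a major secondary endpoint for 2 mg. Section 6.6 places all primary and major secondary endpoints in one graphical procedure at a two-sided family-wise level of 0.05. The figure with the alpha allocation is not visible in the text available for this review.

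**The concern.** The tipping-point analysis is meant to show how robust the primary result is to missing Week 52 data. Two features of its wording can make that result look sturdier than it is.

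**Threshold.** The result being stressed comes from a multiplicity-controlled test, but both the condition for running the grid and the default level of its cells are nominal. Where a dose is tested at less than 0.05, cells between the two thresholds are shown as significant although the controlled conclusion is already lost. A grid can also be produced, with significant cells, for a dose whose hypothesis the graph never rejected.

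**Limits.** The cells that threaten a positive result are those with many placebo switches and few baricitinib switches. If the placebo axis ends at an expected count, some of these cells may not be drawn. The text also leaves a programmer free to build different grids after unblinding.

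**Working it through.** **Inputs from the SAP (section 5.2).** "Study JAIA will randomize approximately 750 patients with a 1:1:1 ratio between baricitinib 4-mg, 2-mg, and placebo", hence 250 per arm. The planning effect is stated as "absolute difference of 17% between a baricitinib treatment group and the placebo treatment group". Placebo response is set at 40% and the test is two-sided at 0.05, hence 40% against 57%.

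**Inputs assumed here.** Placebo responders are set at 100/250 (the planned 40%). Baricitinib responders are varied. The number of switchable missing patients, m, and the local alphas are not given, so ranges are shown.

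**The plan's own figure first.** The stated claim is "The proposed sample size will ensure >90% power". With mean rate p̄ = (0.40 + 0.57)/2 = 0.485:

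power = Φ{[0.17√250 − 1.96√(2 × 0.485 × 0.515)] / √(0.40 × 0.60 + 0.57 × 0.43)} = 0.969.

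This agrees with the plan.

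**Number of hypotheses.** Each dose has seven: SRI-4 at Weeks 52 and 24, LLDAS, corticosteroid sparing, time to first severe flare, Worst Pain and FACIT-Fatigue. Two doses give 2 × 7 = 14. Initial local alphas cannot sum to more than 0.05, so the two SRI-4 Week 52 hypotheses cannot both start at 0.05. At least one depends on alpha passed from other rejections to reach that level.

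**Threshold.** The test is the unadjusted chi-square without continuity correction:

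z = [(b − a)/250] / √[p̄(1 − p̄)(2/250)], p̄ = (a + b)/500,

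where a = 100 + x for x placebo switches, and b is the baricitinib count with no switches. For b = 135:

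| x | z | p |
|---|---|---|
| 0 | 3.136 | 0.0017 |
| 6 | 2.596 | 0.0094 |
| 7 | 2.506 | 0.0122 |
| 9 | 2.326 | 0.0200 |
| 10 | 2.237 | 0.0253 |
| 13 | 1.968 | 0.0491 |
| 14 | 1.878 | 0.0603 |

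The tip is therefore at 7, 10 and 14 switches for alpha 0.01, 0.025 and 0.05. Other baricitinib counts give:

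| Baricitinib v placebo responders | p before switching | Tip at 0.05 | at 0.04 | at 0.025 | at 0.01 |
|---|---|---|---|---|---|
| 125 v 100 | 0.025 | 4 | 3 | 1 | already lost |
| 130 v 100 | 0.0071 | 9 | 8 | 5 | 2 |
| 135 v 100 | 0.0017 | 14 | 13 | 10 | 7 |
| 142 v 100 | 0.0002 | 21 | 20 | 17 | 14 |

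A grid judged at 0.05 places the tip 3 to 4 switches too late if the local alpha is 0.025, 1 too late if it is 0.04, and nowhere too late if it is 0.05.

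**Top limit (baricitinib axis).** Each baricitinib switch moves the tip away. For 130 v 100 at 0.05, the tip is at 9, 13 and 19 placebo switches for 0, 4 and 10 baricitinib switches. The worst row, with no baricitinib switches, is always in the grid, so this limit cannot hide a tip.

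**Right limit (placebo axis).** If it means all switchable placebo patients, nothing is cut off. If it means the expected count, taken as 0.40 × m, then with no baricitinib switches:

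- 133 v 100, m = 25: limit 0.40 × 25 = 10, where p = 0.040; tip at 12 (p = 0.060), which is 12/25 = 48% of missing placebo patients. The tip is not drawn.
- 142 v 100, m = 50: limit 0.40 × 50 = 20, where p = 0.049; tip at 21 (p = 0.060), which is 21/50 = 42%. The tip is not drawn.

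At a 40% response rate, the binomial chance of reaching the tip is 0.27 in the first case and 0.44 in the second. With the same m in the baricitinib arm, the chance that no missing baricitinib patient responds is 0.6^25 ≈ 3 × 10⁻⁶ or 0.6^50 ≈ 8 × 10⁻¹².

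**The case against.** A reader might infer that the grid stops at expectation on both axes and so conceals a plausible overturning of the primary result. The SAP does not support that. The stated expected-number limit is on the baricitinib axis, where it is harmless. The word is not repeated for placebo, and the limit there can equally mean every placebo patient of the same kind. The limits may also be boundaries drawn inside the grid, since they follow the mention of three regions. Even on the truncated reading, the hidden cells need more placebo responses than expected together with almost no baricitinib responses. In the 135 v 100 case with 20 missing per arm, the tip needs 14 of 20 placebo responders (chance about 0.0065 at 40%) and no baricitinib responders. The section already asks for an interpretation of clinical plausibility.

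A reader might also infer that the threshold is certainly too lenient. That is not shown either. The allocation cannot be seen, the power statement uses 0.05, and 4 mg may well be tested at the full 0.05, where nominal and controlled levels coincide. The word nominal is attached only to the condition for running the analysis; 0.05 inside the grid follows from the section 6.4 default.

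Nor is this the only analysis described as a sensitivity analysis for the primary endpoint. Table JAIA.6.1 gives the Per Protocol population that purpose, although Table JAIA.6.6 labels its analysis supplemental.

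What remains is that the rule does not link the grid to the level at which each dose is tested, that the expected number is undefined, and that the placebo limit has two readings.

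**Conclusion.** The point holds in two parts of unequal weight. The main one is the threshold: the rule lets a grid open and be read at nominal 0.05 for a hypothesis tested at a smaller alpha or not rejected at all. In the examples this is worth 3 to 4 placebo switches at a local alpha of 0.025, 7 at 0.01 where the result was significant at that level to begin with, and zero at 0.05. These sizes assume 250 per arm, 40% placebo response and an unadjusted chi-square test.

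The second part is a matter of clarity. The placebo limit can be read in a way that removes overturning cells, but the text does not require that reading, and those cells describe an unlikely pattern of missing responses. The primary analysis itself is unaffected.

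**What to change.** In section 6.10.3.3.1:

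- Run each axis from 0 to all patients in that arm who lack Week 52 SRI-4 without treatment failure. Draw expected counts only as reference lines, and state the rate behind them.
- Judge each cell at the alpha at which that dose's SRI-4 hypothesis was tested in the graphical procedure.
- Label any grid for a hypothesis not rejected there as nominal only.

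The cost is a few sentences of SAP text and a larger grid from the same program. The reported robustness may look slightly less favourable.
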